Using a stepped-wedge cluster randomized trial (RCT), we will evaluate the effects of this stepped care depression model, the protocol of which this paper describes in detail. The primary objective of the study is to assess whether the integrated depression care model is superior to usual care on (1) reducing depression symptoms and functional impairment (primary outcomes); (2) improving physical health for those with HIV, diabetes and/or hypertension (secondary outcomes); and (3) reducing perceived mental health stigma and increasing retention in IC3 care (care processes). We will also evaluate the incremental cost-effectiveness of integrating evidence-based depression care, relative to usual care, and track mental health-related outcomes among household members of patients. If efficacious and cost-effective, this study will provide a model for integrating depression care into HIV clinics in Malawi, and the study will promote social wellbeing among household members.

METHODS

Study Design

This is a prospective, stepped-wedge cluster randomized trial to evaluate the effects of an evidence-based depression care model, relative to usual care, on mental and physical health outcomes of patients seeking care at integrated chronic care centers (IC3) in Neno, Malawi. The study will take place at fourteen health clinics in Neno District, which will constitute our clusters. Clinics will be randomized to one of five arms, each comprising 2-3 health clinics, such that the clinics receive the intervention in a random order and all clinics receive the intervention by the end of the study (Figure 1).

Figure 1. Stepped wedge design of IC3D clinical trial

Period	Period 1			Period 2			Period 3			Period 4			Period 5			Period 6			Period 7			Period 8			Period 9			Period 10		
Month	1	2	3	4	5	6	7	8	9	10	11	12	13	14	15	16	17	18	19	20	21	22	23	24	25	26	27	28	29	30
Arm 1	Pre	Pre	Pre	Int	Int	Int	Post	Post	Post	Post	Post	Post	Post	Post	Post	Post	Post	Post	Post	Post	Post	Post	Post	Post	Post	Post	Post	Post	Post	Post
Arm 2	Pre	Pre	Pre	Pre	Pre	Pre	Int	Int	Int	Post	Post	Post	Post	Post	Post	Post	Post	Post	Post	Post	Post	Post	Post	Post	Post	Post	Post	Post	Post	Post
Arm 3	Pre	Pre	Pre	Pre	Pre	Pre	Pre	Pre	Pre	Int	Int	Int	Post	Post	Post	Post	Post	Post	Post	Post	Post	Post	Post	Post	Post	Post	Post	Post	Post	Post
Arm 4	Pre	Pre	Pre	Pre	Pre	Pre	Pre	Pre	Pre	Pre	Pre	Pre	Int	Int	Int	Post	Post	Post	Post	Post	Post	Post	Post	Post	Post	Post	Post	Post	Post	Post

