Integrating a Stepped Care Model of Screening and Treatment for
Depression into Malawi's National HIV Care Delivery Platform

(ID: R01MH117760)

Statistical Analysis Plan

Analysis of Primary Outcomes

This analysis plan concerns the primary outcomes of the IC3D intervention trial. However, analyses of the secondary outcomes will follow the same procedure with appropriate changes for the nature of the outcome.

We will have primary outcomes at two levels. At the aggregate cluster-time level we have

1. Prevalence of depression

As we do not capture data on those who do not have depression that would enable us to link individual screening outcomes between time periods, we will only be able to collect total number screened and total number with depression for each cluster at each time period (i.e. "step").

At the individual level, among those who are diagnosed with depression we will collect:

2. Depression severity among those with depression (PHQ-9)
3. WHODAS score among those with depression
4. EQ-5D-3L utility score and those with depression

If the intervention is successful then it should have the effect of reducing the overall prevalence of depression among those with chronic conditions, and also reduce the severity of depression and improve the quality of life among those with depression in this group of patients.

The data derived from the trial will be analysed using a generalised linear mixed model framework standard for stepped-wedge cluster designs.[1] Several trial guidelines, including the influential CONSORT statement,[2,3] recommend the specification of a single primary outcome to avoid a multiple comparisons problem. However, given the complex, multifaceted nature of this health service delivery intervention, no single outcome can adequately describe the effect of the intervention and be used to judge its effects. As a result, we have specified several primary outcomes and will "correct" or modify our analyses to account for the multiple outcomes problem.

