There are two main types of approach to dealing with multiple outcomes: multivariate methods and univariate methods. The former method works by jointly modelling all the outcomes at once. However, the joint model of the four outcomes is highly complex, potentially with non-linear sub-models, two-stage models, and shared random effects to allow for correlation (see Appendix), which makes inference difficult or even infeasible without development (and evaluation) of custom software (e.g. a Monte Carlo Maximum Likelihood sampler), which is out of the scope of this project. Instead, we will model the outcomes separately and use a method to correct the family-wise error rate (a univariate methodology).

Statistical model

Aggregate cluster-time outcome

For cluster $j = 1, \dots, J$ at time period $t = 1, \dots, T$ we will screen n_{jt} patients of whom $y_{jt}^{(1)}$ will be diagnosed with depression such that

$$y_{jt}^{(1)} \sim \text{Binomial}(n_{jt}, p_{jt})$$

where we will specify a logistic regression model:

$$\log\left(\frac{p_{jt}}{1-p_{jt}}\right) = z'_{jt}\gamma_1 + \delta_1 D_{jt} + \alpha_{j,1} + \phi_{jt,1}$$

where z_{jt} is a vector of cluster-level covariates, and $\alpha_j \sim N(0, \sigma_\alpha^2)$ and $\phi_{jt} \sim N(0, \sigma_\phi^2)$ are cluster and cluster-time random effects, respectively.

Individual-level outcomes

For patient $i = 1, \dots, N$ who has depression the outcome is $y_{ijt}^{(k)}$ for outcomes $k = 2, 3, 4$. For each outcome we specify the linear model:

$$y_{ijt}^{(k)} = x'_{ijt}\beta_k + z'_{jt}\gamma_k + \delta_k D_{(i)jt} + \theta_{i,k} + \alpha_{j,k} + \phi_{jt,k} + e_{ijt,k}$$

where x_{ijt} is a vector of patient-level covariates $\theta_i \sim N(0, \sigma_\theta^2)$ is an individual-level random effect and e_{ijt} is an independent, identically distributed error term.

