The implementation outcomes are divided into three categories:

1. Screening:
 - a. Proportion of patients screened with the PHQ-2, out of those attending IC3 clinics.
 - b. Proportion screening positive with PHQ-2, out of those who were administered the PHQ-2.
 - c. Proportion screened on the PHQ-9, out of those who screened positive on the PHQ-2.
 - d. Proportion screening positive on PHQ-9, out of those who were administered the PHQ-2.
2. Diagnosis:
 - a. Proportion of patients who are administered the BDIS, out of those who screened positive on the PHQ-9.
 - b. Proportion of patients who receive a diagnosis using BDIS, out of those administered the BDIS.
3. Treatment:
 - a. Proportion of patients attending treatment sessions (PM+, ADT, both), out of those who have been enrolled in the IC3D clinical trial and elected to receive treatment (PM+, ADT, both)
4. Protocol Fidelity:
 - a. Proportion of reviewed mastercards appropriately completed by clinical officers
 - b. Proportion of patient registration forms appropriately completed by counsellors
 - c. Proportion of PM+ components appropriately covered within each PM+ therapy session

Each step is a potential point of failure that could limit the acceptability or effectiveness of the intervention. Analysis of the implementation outcomes constitutes a descriptive analysis intended to support interpretation of trial results.

We will report the overall trial mean proportions of each implementation outcome along with 95% confidence intervals. Note that the screening and diagnosis outcomes are available for both treatment and control conditions, while the treatment outcomes are only available in treatment units. We will also examine the temporal changes in the implementation outcomes by reporting within each three-month block mean proportions and associated uncertainty intervals.

Secondary analyses

In addition to the usual issues of adherence, such as patients refusing treatment or not attending scheduled treatment, we have identified that patients diagnosed in one month or trial “block” may not be treated until the subsequent month or trial block. At an individual level, non-adherence would

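### Screening and diagnosis proportions are planned only as pooled overall and three-month means, so a change in case-finding when clinics switch could not be separated from a calendar trend

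*SAP*

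**What the plan says.** The SAP addendum of 18 November 2021, under Implementation outcomes, lists screening items 1a-1d, diagnosis items 2a-2b, a treatment item and protocol fidelity items. Two summaries are planned:

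- Overall: "We will report the overall trial mean proportions of each implementation outcome along with 95% confidence intervals".
- By calendar block: "We will also examine the temporal changes in the implementation outcomes by reporting within each three-month block mean proportions and associated uncertainty intervals".

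Neither is split by condition, yet the same paragraph says: "Note that the screening and diagnosis outcomes are available for both treatment and control conditions". Treatment outcomes are said to exist only in treatment units. No formula or model is named for the intervals. The purpose is given as follows: "Analysis of the implementation outcomes constitutes a descriptive analysis intended to support interpretation of trial results".

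The related primary outcome is in the SAP under Analysis of Primary Outcomes. For prevalence the trial collects the "total number screened and total number with depression for each cluster at each time period". The model under Aggregate cluster-time outcome is a binomial logistic regression with the treatment indicator D_jt and two random terms, which "are cluster and cluster-time random effects, respectively". The printed equation shows no explicit period term. The protocol's model, under Analysis of Intervention Effects, does have time fixed effects.

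On the design, Protocol, Study Design states: "The study will take place at fourteen health clinics in Neno District, which will constitute our clusters". Clinics are allocated to five arms of two or three clinics that switch three months apart (Figure 1).

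**The concern.** The implementation items describe how patients enter the primary analysis. Outcome 1 is the number with depression over the number screened, and outcomes 2-4 are recorded only in patients who screen positive. If the share of patients completing a step changes when a clinic switches, the primary estimates can move with no change in the underlying illness.

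The documents give reasons to look. Counsellors administer the PHQ-9 and the diagnostic interview, and psychosocial counsellors also deliver PM+. The protocol concedes under Randomization, Allocation and Blinding that unblinded participants may report differently. A summary meant to help interpret the trial should show whether case-finding moved with the intervention. In a stepped wedge, pooling over conditions within calendar time removes the comparison that would show this.

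**Working it through.** **1. Inputs.** There are 14 clinics in five arms of 2-3, so four arms have three clinics and one has two. Steps are three months and the principal analysis covers months 1-18, that is six periods (Protocol, Study Design and Analysis of Intervention Effects). Sample Size assumes 30 enrollees per facility per step, 10% depression prevalence and ICC 0.05. Its total reproduces: 14 x 30 = 420. The addendum gives no interval width to reproduce. I count a clinic as switched from its first intervention month in Figure 1.

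**2. Share of clinics switched, periods 1-6.**
- Two-clinic arm last: 0, 3/14, 6/14, 9/14, 12/14, 1 = 0, 0.21, 0.43, 0.64, 0.86, 1.
- Two-clinic arm first: 0, 2/14, 5/14, 8/14, 11/14, 1 = 0, 0.14, 0.36, 0.57, 0.79, 1.

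In either order the correlation with linear time is 0.998.

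**3. What the planned summaries would show.** Suppose, for illustration, that a proportion jumps from 10% to 15% at switch-over with no calendar trend. Block mean = 10 + 5 x share switched. Compare this with a pure calendar rise of 1 point per period and no effect of switching (two-clinic arm last):

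| Period | 1 | 2 | 3 | 4 | 5 | 6 |
|---|---|---|---|---|---|---|
| Jump at switch, % | 10.0 | 11.1 | 12.1 | 13.2 | 14.3 | 15.0 |
| Calendar trend only, % | 10 | 11 | 12 | 13 | 14 | 15 |

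The largest gap is 14.29 - 14 = 0.29 points. The overall mean under the jump is 12.4-12.6% over six periods and 13.4-13.6% over the ten periods of Figure 1. It cannot show the change at all.

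**4. What a split by condition would show.** In periods 2-5 both conditions coexist. Under the jump, control clinics stay at 10% and intervention clinics at 15% in each of these periods. Under the trend, both groups read 11, 12, 13, 14%. The two explanations come apart. Periods 1 and 6 carry no contrast, because all clinics are in one condition.

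**5. Why the outcome 1 model does not fill the gap.** Take outcome 1 as diagnosed patients over patients given the PHQ-2, which is one reading of the SAP model section. It is then the product of items 1d, 2a and 2b. Suppose, purely as an illustration, that item 2a falls from 90% to 75% at switch-over while true depression is unchanged and outcome 1 starts at 10%. Outcome 1 becomes 0.10 x 0.75/0.90 = 8.3%, an apparent odds ratio of (0.0833/0.9167)/(0.10/0.90) = 0.82. The model would attribute this to the intervention.

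**6. Intervals, only if they were simple binomial.** For one block, the design effect is 1 + (m - 1) x ICC, and the factor by which the interval is too narrow is its square root.
- m = 30: 1 + 29 x 0.05 = 2.45, factor 1.6.
- m = 300 (assumed, from 30/0.10): 1 + 299 x 0.05 = 15.95, factor 4.0. At a proportion of 10%, the half-width is 1.96 x sqrt(0.09/4200) = 0.9 points unadjusted and 3.6 points adjusted.
- m = 300 with ICC from 0.005 to 0.10: factor 1.6 to 5.6.

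Even the unadjusted 0.9 points exceeds the 0.29-point gap in step 3, so the block means could not discriminate with either interval.

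**The case against.** The strongest reply is that this is a declared descriptive addendum which alters no primary estimand or test, that screening applies in both conditions by design, and that no shift in case-finding has been shown. The data exist for both conditions, so a table could be made later. Outcome 1, which is close to item 1d, is already contrasted by condition. All of this is fair and limits the weight of the point. It does not remove it. A split by condition is still descriptive, a table chosen after the results carries less weight than one planned now, and outcome 1 is the quantity whose interpretation is in question. Items 1a-1c and 2a-2b have no contrast by condition anywhere.

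Two stronger readings are tempting and are not supported.

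- A reader might infer that the plan gives a single overall figure and would make a switch-over change invisible. It does not: block means are planned, and in step 3 they move from 10% to 15%. The defect is that the movement is aliased with calendar time.
- A reader might infer that precision is overstated, perhaps by a large factor if the 13,000 patients served in 2020 are spread over 14 clinics. The SAP names no interval method, and it says that secondary outcomes follow the primary procedure with suitable changes, so clustered intervals may be intended. The 13,000 is a year's whole caseload, not the number screened in a block, and ICC 0.05 was chosen for the primary outcomes. The documents support only that the method is unstated.

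**Conclusion.** The point holds as a worthwhile, inexpensive improvement to a secondary analysis. As planned, a change in screening coverage or diagnostic yield at switch-over would appear in the block means but could not be told from a calendar trend (correlation 0.998, gap at most 0.29 points in the illustration). For that question the stated purpose is not met.

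The aliasing rests only on the Figure 1 roll-out and the 14 clinics, assuming that clinics weigh equally. Unequal clinic sizes would change the ramp's shape, but the block means would still pool the two conditions. The 10%/15% and 90%/75% figures are illustrations, not predictions. The possible understatement of interval width (1.6-fold with 30 patients per clinic, about 4-fold with an assumed 300, in one block at ICC 0.05) is conditional on simple binomial intervals, which the SAP does not say it will use. That part is a minor clarification.

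**What to change.** - For items 1a-1d and 2a-2b, report each proportion by condition within each three-month period.
- Add a descriptive intervention-control difference from a logistic mixed model with D_jt, period effects written out explicitly, and clinic and clinic-period random effects. The period terms must be named, because the SAP's outcome 1 equation does not show them.
- Keep the overall and block means as planned, and say which months the overall mean covers.
- Do not fit D_jt for the treatment and fidelity items. The SAP claims data in both conditions only for screening and diagnosis.
- State that all implementation intervals allow for clinic clustering, and name the method.

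The cost is SAP wording and a few extra fits, provided numerators and denominators are held by clinic and period. Intervals may be wider, and some cells will rest on only two or three clinics (periods 2 and 5). One limit remains. Items 1a, 1c and 2a measure whether a step was carried out and will show a change in process directly. Items 1b, 1d and 2b still mix reporting or case-finding with true prevalence, so the split narrows the ambiguity without removing it. No primary estimate changes.

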APPENDIX

Multivariate model

Given that the outcomes are mixed discrete and continuous, we will use a shared random effects approach to jointly model the outcomes. For patient $i = 1, \dots, N$ in cluster $j = 1, \dots, J$ at time period $t = 1, \dots, T$ the outcome is $y_{ijt}^{(k)}$ for outcomes $k = 1, 2, 3, 4$. For each outcome we specify the linear predictor:

$$\eta_{ijt}^{(k)} = x'_{ijt}\beta + z'_{jt}\gamma + \delta_k D_{(i)jt} + \psi_{k,\theta}\theta_i + \psi_{k,\alpha}\alpha_j + \psi_{k,\phi}\phi_{jt} \quad (3)$$

where x_{ijt} is a vector of patient-level covariates, z_{jt} is a vector of cluster-level covariates, $\alpha_j \sim N(0, \sigma_\alpha^2)$, $\phi_{jt} \sim N(0, \sigma_\phi^2)$ and $\theta_i \sim N(0, \sigma_\theta^2)$ are cluster, cluster-time, and individual-level random effects, respectively, and $\psi_{k,\cdot}$ are factor loadings with $\psi_{1,\cdot} = 1$ for identifiability. The parameter of interest is δ_k . We will take both intention to treat (ITT) and per protocol approaches. For the ITT analysis, the variable D_{jt} is an indicator equal to one if cluster j is in the intervention state at time t and zero otherwise. Thus, δ represents our estimated treatment effect. For the per protocol analysis, D_{ijt} will be a patient-level variable equal to one if the clinic was in the intervention state and the patient completed the treatment as defined above, and zero otherwise.

For each outcome, $y_{ijt}^{(k)}$, we specify its distribution with probability density function

$$f_k\left(y_{ijt}^{(k)}; \theta, \Phi\right)$$

where $f_k(\cdot)$ is a probability density function, $g_k(\cdot)$ a link function and θ is set of all model parameters and Φ are the random effect terms. For outcome 1 we specify a Binomial-logistic model, and for the other outcomes a linear model with normally-distributed errors.

Outcomes 2-4 described above are only recorded for those who screen positive for depression at their scheduled visit as these instruments are not used for other patients in the trial. For each time period (quarterly), any patient eligible for screening (i.e. in the "denominator population") will have a value for recorded for Outcome 1 equal to one if they screen positive and meet the pre-defined criteria for entry into the depression care programme, or zero otherwise. The model is thus a "two-stage" type model with only those with defined depression contributing data from Outcomes 2-4 to the likelihood. Letting Y represent all the data, the log-Likelihood is therefore:

$$\begin{aligned} \log L(\theta|Y, \Phi) &= \log f(Y; \theta, \Phi) \\ &= \sum_{i=1}^n \left(1 - y_{ijk}^{(1)}\right) \log\left(1 - g_1\left(\eta_{ijt}^{(1)}\right)\right) \\ &\quad + y_{ijk}^{(1)} \left(\log\left(g_1\left(\eta_{ijt}^{(1)}\right)\right) + \log f_2\left(y_{ijt}^{(2)}; \theta, \Phi\right) + \log f_3\left(y_{ijt}^{(3)}; \theta, \Phi\right)\right) \\ &\quad + \log f_2\left(y_{ijt}^{(3)}; \theta, \Phi\right) + \log f_\phi(\Phi; \omega) \end{aligned}$$

where ω are the parameters of the joint distribution of random effects. The likelihood function for the parameters alone is determined by integrating out the random effects Φ and then maximising the resulting likelihood. Given the complexity of our model including non-linear effects, two-stage models, and multiple shared random effect terms, there exists no "out of the box" software that could reliably be used. Instead an alternative approach, such

as Monte Carlo Maximum Likelihood would be required. Given the technical complexity required, and any simulation-based testing that would be required to ensure any custom-built sampler was functioning correctly, we instead opted for a univariate methodology.
